[name]

Ospemifene versus Conjugated Estrogens in the Treatment of Postmenopausal Sexual Dysfunction

[name]

Female Pelvic Medicine and Reconstructive Surgery, Fellow
Emory University

[name], PhD

Female Pelvic Medicine and Reconstructive Surgery, Division Director & Fellowship Director
Associate Professor
Emory University Hospital, Chief of Service

[name], MPH, NCMP

Department of Obstetrics & Gynecology, Associate Professor
Menopause Clinic, Director
Emory University

Abstract & Relevance

57% of postmenopausal women suffer from female sexual dysfunction (FSD). Vulvovaginal atrophy (VVA) is a condition that impacts up to 60% of the growing postmenopausal female population, and the most common symptom is dyspareunia. Women with FSD are 3.84 times as likely to also have VVA. Vaginal estrogen is the most common treatment for VVA, but it only marginally improves overall sexual function, and many women and clinicians avoid using it because of the risks of exogenous estrogen use during menopause. Ospemifene is a SERM that is FDA-approved for dyspareunia related to VVA, and has shown superb improvements in overall sexual health. This oral medication, taken daily, improves vaginal health, and has demonstrated protective activity in the breast and bone tissues. It also has not demonstrated any carcinogenic activity in the endometrium or liver. This study hopes to determine if ospemifene is superior to conjugated estrogens in improving sexual function and vaginal atrophy symptoms. 104 women will be randomized to receive 12 weeks of 60mg oral ospemifene, taken daily, or 12 weeks of 0.5mg vaginal conjugated estrogens, which is placed vaginally twice per week. The improvements in sexual health and VVA symptom severity will be compared in each group. This study will help determine if ospemifene is a better treatment medication than conjugated estrogens. The implications of this study may provide an attractive alternative to the many women who continue to suffer from sexual dysfunction and VVA because of concerns surrounding the use of exogenous hormones.

Introduction

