All research activities will be performed after obtaining Institutional Review Board Approval from Emory University. A consecutive sample of women will be recruited from the FPMRS and Menopause patients within The Emory clinics. Subjects are identified after their management plan has been established to include treatment of vulvar and/or vaginal atrophy. Patients will be approached by the principal and/or co-investigators. For women that agree to participate, written informed consent will be obtained. All women who agree to participate in this study must meet inclusion criteria listed in Table 1. Once the exclusion criteria have been applied (Table 2), the qualifying subjects will be enrolled in the study. Once enrolled, each subject will complete the Female Sexual Function Index (FSFI) questionnaire and a symptom severity Likert scale. Finally, they will receive instructions on medication compliance, as well as potential adverse events for the designated medication. If we assume 50% of women offered enrollment in this study will agree and be eligible to participate, we expect to reach our target enrollment in seven to eight months.

Table 1. Inclusion Criteria
Interested in resuming or continuing sexual activity

Table 1. Inclusion Criteria

Greater than 12 months since last menstrual cycle or prior bilateral oophorectomy
40yo or older
Dyspareunia as a vulvovaginal atrophy symptom
Normal mammogram within 12 months prior to entry into the study

Table 2. Exclusion Criteria

History or suspicion of breast carcinoma
History of hormone-dependent tumor
Genital bleeding of unknown cause
Ongoing vaginal infection
History of CVA, MI or heart disease, uncontrolled HTN over 160/100
Serious disease or chronic condition that may prevent completion of study, BMI over 40
Hypercoagulable state, or currently on anticoagulant therapy
Use of any exogenous sex hormone within three months from study entry, or during the study
Pelvic surgery within the last 12 months

Randomization and Allocation Concealment

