Once a qualifying subject is identified, she will be randomized into a treatment group. The participant will be randomized to receive either a vaginal conjugated estrogens prescription or an ospemifene prescription. A computerized randomization program will be used to perform block randomization in random blocks of 4 and 10. Allocations envelopes containing the assignment will be used for the study. They will be sealed opaque envelopes with aluminum foil inside. They will also contain carbon-copy paper. The treatment number will be printed on the envelope. Once the participant has signed the informed consent form, her name will be printed on the envelope, which will transfer over to the carbon-copy paper, and the envelope will be opened.

Study Plan

The patient will be informed of her assigned medication, and she will receive a medication coupon to help offset the cost of the medication. Each medication is FDA-approved for long-term use of at least 52 weeks. For this study, a 12-week prescription for the medication will be sent electron-

[figure not shown]
ically to the pharmacy of her choice. Treatment with estrogen will consist of 0.5 gram of conjugated estrogens placed vaginally for 12 weeks. Treatment with ospemifene will consist of a 60mg tablet that will be taken at the same time daily for 12 weeks.

The patient will receive an intake packet that includes the following information:

1. Copy of signed informed consent form
2. Important contacts and instructions for emergency/adverse events
3. Allocation card
4. Medication's FDA packet insert
5. Instructions on dosing
6. 12-week date to repeat questionnaires

She will be called the following day to confirm her start date of the medication. They will return at 12 weeks and complete the same FSFI and Likert Scale questionnaires regarding sexual function and VVA symptoms. The questionnaires may also be completed over the phone with the investigator.

Alternatively, if time during clinic is limited, the patient can be consented and allocated to a medication in person, by a co-investigator. She will be called by a co-investigator on the same day to complete the enrollment and questionnaires. Below is a summary of the study plan.

Sample Size Analysis

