To our knowledge, there has been no prior study that reported the prevalence of female sexual dysfunction amongst women using vaginal conjugated estrogens, defined as having an FSFI score of 26.55 or less. With an FSD prevalence of 57%, we determine a 50% reduction in the prevalence to be clinically significant. Setting an alpha of 0.05, and a power of 0.80, and assuming a minimum of 15% dropout rate, the sample size is set to 52 in each group.

Specific Aims

Specific Aim 1: To compare the efficacy of each drug in improving sexual function.

- a. Experimental Design: In this study, participants will be asked to complete the 19-question female sexual function index (FSFI) questionnaire at the beginning of the study period and at 12 weeks. The results will be used to compare the effect of each medication on the various domains of sexual function.

The mean total score in each treatment group at baseline will be compared using Student's t-test. Additionally, the score of the components of desire, arousal, lubrication, orgasm, satisfaction and pain will be similarly compared. Later, the change in these scores between the two treatment groups at 12 weeks will be compared using a paired t-test analysis.

Anticipated Results and Interpretation: We expect to see similar results in this study, showing comparable improvements in vaginal lubrication and dyspareunia, while showing greater improvement for overall sexual health in the ospemifene group.

Potential Pitfalls, Alternative Approaches, and Future Directions: We do not anticipate any challenges with the administration and analysis of this questionnaire.

Specific Aim 2: To compare each drug's impact on VVA symptoms

- a. Experimental Design: Participants will complete a Likert scale of symptom severity at the beginning and at the end of the study. The symptoms listed will include dyspareunia, vaginal dryness, vaginal pain, and vaginal itching. The survey will ask them to rate the severity of each VVA symptom on a scale of 0 to 3, with 0 being none, 1 being mild, 2 being moderate, and 3 being severe. It will also ask them to choose their most bothersome symptom (MBS).

The mean score of the MBS in each treatment group at baseline will be compared using Student's t-test. Later, the change in score of the MBS between the two treatment groups at four weeks and again at 12 weeks will be compared using a paired t-test analysis.

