Anticipated Results and Interpretation: Similar to objective findings, prior studies have shown significant improvement in VVA symptoms in patients using ospemifene or vaginal estrogen. We anticipate that the improvements seen with ospemifene will be comparable to those seen with vaginal estrogen.

Potential Pitfalls, Alternative Approaches, and Future Directions: The Likert scale is commonly used to assess symptom improvement in VVA treatment studies. We do not anticipate any pitfalls in this specific aim.

Safety Monitoring

Participants in the study will be provided with contact information to be used in the case of an adverse event related to the medication. For emergencies, they will be instructed to dial 911 and/or seek immediate medical attention. They will be instructed to contact the study team at [contact], to inform the team about any adverse event that may be related to the medication.

All reports of injury will be logged in one password-protected electronic file, by members of the study team. Patient data, including adverse events will be reviewed every two weeks by the [name] and [name]. Appendix 1 shows adverse events that have been documented during prior clinical trials of the two medications. This data will be used to determine whether the study will be discontinued due to occurrence or frequency of any given adverse event.

Individual Stopping Rules

Any event that involves new onset of vaginal bleeding, cardiovascular event, venous thromboembolism, or new diagnosis of cancer, will require the individual to discontinue the medication and withdraw from the study.

Timeline

Item	Start	Complete/Submit
IRB application	Started	November 1, 2016
Grant/Funding applications	Started	February 2017
Subject recruitment	November 1, 2016	August 1, 2017
Data Analysis	March 1, 2017	August 30, 2017
Thesis/Report	November 15, 2017	December 1, 2017

Required Resources & Budget

Resource	Estimated Cost
Personnel	
Consent forms, severity scale, questionnaire, other paper documents	
Counseling office	

\$10 gift cards for return visit, 104 subjects	\$1040.00
--	-----------

References

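### The Timeline closes data analysis before the last 12-week outcome can exist, and opens it five months before recruitment ends without saying what is analysed

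*Combined protocol and SAP*

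**What the plan says.** Three rows of the Timeline matter: "Subject recruitment November 1, 2016 August 1, 2017", "Data Analysis March 1, 2017 August 30, 2017" and "Thesis/Report November 15, 2017 December 1, 2017".

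The Study Plan sets the outcome visit: "They will return at 12 weeks and complete the same FSFI and Likert Scale questionnaires".

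Patient Groups gives a shorter recruitment forecast than the Timeline's nine months: "we expect to reach our target enrollment in seven to eight months".

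Sample Size Analysis takes a 57% prevalence of sexual dysfunction, treats a halving as clinically significant, and continues: "Setting an alpha of 0.05, and a power of 0.80, and assuming a minimum of 15% dropout rate, the sample size is set to 52" per arm, which is 104 in total.

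The Approach overview says that participants and clinicians cannot be blinded. Safety Monitoring provides for patient data to be reviewed every two weeks. No section describes an interim analysis, a data lock or a condition for starting the final analysis.

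**The concern.** The recruitment row, the analysis row and the 12-week endpoint cannot all be followed if recruitment uses the window it is given. Some women would still be on treatment when analysis is due to be complete. An analysis actually closed on 30 August 2017 would lack their scores, on top of the dropout already allowed for.

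The second issue is the start date. Analysis opens on 1 March 2017 with five months of recruitment left. Investigators approach patients, know the assignments and may take the questionnaires by phone, and the primary outcome is self-reported. If between-arm results were seen in that period, they could affect who is approached, how questionnaires are taken, or when enrolment stops. The plan does not rule this out, because it does not say what the early analysis consists of.

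**Working it through.** **Inputs.** Recruitment 1 November 2016 to 1 August 2017, analysis 1 March to 30 August 2017, report start 15 November 2017 (Timeline). Outcome at 12 weeks = 84 days (Study Plan). Enrolment forecast of seven to eight months (Patient Groups). 52 per arm, alpha 0.05, power 0.80, dropout 15%, 57% v 28.5% (Sample Size Analysis). Uniform accrual is my assumption; the documents give no accrual pattern.

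**1. The plan's own sample size.** Neither formula nor sidedness is stated. The two-sided unpooled normal approximation gives

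n = (1.960 + 0.842)² × (0.57 × 0.43 + 0.285 × 0.715) / 0.285² = 7.849 × 0.4489 / 0.0812 = 43.4, so 44 per arm.

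Then 44 / 0.85 = 51.8, so 52. This matches the plan. The pooled two-sided version gives 47, or 56 after dropout, and does not match.

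**2. Dates.**
- Last possible outcome: 1 August 2017 + 84 days = 24 October 2017.
- That is 55 days after the analysis close and 22 days before the report start.
- Latest enrolment with an outcome by the close: 30 August 2017 − 84 days = 7 June 2017.

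**3. Women without a 12-week score on 30 August 2017.** Share = days of enrolment after 7 June / total days of enrolment. The last column is 52 × (1 − share) × 0.85.

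| Enrolment ends | Days | Days after 7 June | Share | Women of 104 | Left per arm after 15% dropout |
|---|---|---|---|---|---|
| 1 June (7 months) | 212 | 0 | 0% | 0 | 44.2 |
| 1 July (8 months) | 242 | 24 | 9.9% | 10 | 39.8 |
| 1 August (9 months) | 273 | 55 | 20.1% | 21 | 35.3 |

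With a seven-month enrolment the last outcome falls on 24 August 2017, just inside the close.

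**4. Power, only if those women were left out.** For 57% v 28.5%, two-sided alpha 0.05, the unpooled formula is Φ(0.285 / √(0.4489 / n) − 1.960).

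| n per arm | Unpooled | Pooled |
|---|---|---|
| 44.2 | 81% | 78% |
| 39.8 | 77% | 74% |
| 35.3 | 71% | 68% |

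These figures concern the comparison of proportions used for sizing. Specific Aim 1 plans t-tests on FSFI scores, so they are not the power of that analysis.

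**5. Overlap with recruitment.** From 1 March to 1 August 2017 is 153 days, and 153 / 273 = 56% of the recruitment window. With nine-month uniform accrual, 120 / 273 × 104 ≈ 46 women would be enrolled on 1 March, and 36 / 273 × 104 ≈ 14 would have reached week 12.

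**The case against.** The strongest reply is that the table is a rough planning schedule and not an operative rule. It starts recruitment on the day the IRB application is due, although Patient Groups requires approval first. The document is marked as updated on 27 November 2017, after every Timeline date except the report deadline. This limits the practical risk. It does not remove the inconsistency: the table stands in the current text, and nothing else says when outcome analysis may begin.

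A reader might infer that about a fifth of the women will be lost, that the sample size cannot be delivered and that 80% power is missed. The documents do not support this. No section sets a cutoff that excludes late recruits. The intake packet gives each woman a 12-week date, the budget covers return-visit gift cards for 104 subjects, and the report starts after the last possible outcome. A fifth is also the upper end of the range; under the protocol's own forecast the share is 0% to 10%.

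A reader might also infer that arms are compared while women are still being enrolled. The row says only that data are analysed. Data preparation or baseline description would fit a March start, and Specific Aim 1 places the 12-week comparison after the baseline one. The tests listed there are all between treatment groups, so an early between-arm look is possible, but it is not stated. Consecutive recruitment, sealed opaque envelopes and a fixed sample size also limit what such a look could influence.

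**Conclusion.** The point holds as a minor inconsistency. On the stated dates, analysis is due to close up to 55 days before the last 12-week outcome, and it opens 153 days before recruitment ends with its content and audience undefined.

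Followed literally, the schedule would leave 0% to 20% of the 104 women without a score at the close, depending on whether enrolment takes seven, eight or nine months and assuming uniform accrual. The corresponding power for the sizing comparison runs from 81% down to 71% (unpooled) or from 78% to 68% (pooled), and the lower figures apply only if those women were excluded. The likelier explanation is a wrong or outdated analysis row, not an intention to drop late recruits or to look early.

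**What to change.** Reconcile the Timeline with the 12-week visit in the Study Plan and with the enrolment forecast in Patient Groups. Define the start of outcome analysis by an event instead of a calendar date: the last enrolled woman's 12-week questionnaire. On the stated dates that is no earlier than 24 October 2017.

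Add one sentence stating that no between-arm comparison of FSFI or symptom scores is run before that point, and that earlier work is limited to data entry, cleaning and the existing two-weekly safety review.

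The cost is one table row and one sentence. The downside is a shorter analysis window, about three weeks (22 days) before the report start on the stated dates, or a slightly later report.

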Appendix 1. TEAEs in Vaginal Conjugated Estrogens Cream and Ospemifene Trials				
	Ospemifene 60mg x 12 weeks [17]	Ospemifene 60mg x 52wks [7]	Vaginal CE 0.3mg x 12 weeks [30]	Vaginal CE 0.3mg x 52 weeks [30]
% w/ 1 or more TEAE	Not stated, 1892 exposed patients total, 1000 patient years of exposure	63.8%	71.4%	61.4%
Headache	2.4%		18.6%	14.4
Muscle spasm	3.2%			
Arthralgia				9.1
Vaginal discharge	3.8%			
Vaginal candidiasis or mycotic infection		4.3%		
Vaginitis				6.1%
Hot flashes	7.5%	7.2% (1.6% discontinuation rate)		
UTI	Similar to placebo	8.7% (8.2% for placebo)		
Vaginal bleeding			*1.4% of all groups	*1% of all groups
Proliferative endometrium				0.08%
Hyperplasia or cancer	0%	0%		0%
Cardiovascular events/VTE	0.3%	0%		
URI/Nasopharyngitis/Sinusitis		5% or more		
Pharyngolaryngeal pain		5% or more		
Hypercholesterolemia		5% or more		
Serious/Severe TEAEs <5%	0.13 per patient year (0.21 in placebo group)	5 participants with 7 TESAEs: breast prosthesis implantation, encephalitis herpes, non-cardiac chest pain, candida meningitis, gastritis, chronic obstructive pulmonary disease, and dehydration	5 participants from all groups, considered unrelated to study	6 participants from all groups, considered unrelated to study
TEAE: treatment-emergent adverse event; CE: conjugated estrogens; VTE: venous thromboembolism; *: study does not distinguish between placebo and the two treatment arms.
